10.3.2.1 Elective Surgery/Routine Examination

Elective surgery (a planned, non-emergency medical procedure) and in-patient routine examination for a pre-existing condition (i.e., recorded in the medical history) do not qualify as SAEs as long as the procedure was not performed as a result of a worsening of the condition. In addition, hospitalisation for the purpose of study drug administration should not be recorded as an SAE. However, AEs which occur during the (elective) hospitalisation will need to be collected and reported.

10.3.3 Pregnancy

The safety of study treatment in pregnant women needs to be monitored once study treatment has been administered to them (as per protocol, pregnancy is an exclusion criteria). Therefore, the outcome of all such pregnancies (including normal births) must be followed up and documented, even if the subject was withdrawn from the study.

Women of childbearing potential should have a negative serum pregnancy test at screening and at the End of Study Visit. Study medication should not be initiated by the Investigator until a report of a negative pregnancy test has been obtained.

Effective contraception must be used before beginning study medication, during study dosing, and for 1 month following discontinuation of study medication.

A female subject must immediately inform the Investigator if she becomes pregnant during the study and be instructed to stop taking study medication. The Investigator should counsel the subject and discuss the risks of continuing with the pregnancy and the possible effects on the foetus.

The Investigator/Sponsor is responsible for monitoring the subject and pregnancy outcome. Every effort should be made to gather information regarding the pregnancy outcome until 90 days postpartum (or otherwise as appropriate). It will be the responsibility of the Sponsor, together with the appropriate support of the Investigator, to obtain this information.

A male subject must immediately inform the Investigator if his female partner becomes pregnant during the study. The female partner of a male subject should also be counselled and followed-up as described above.

Any report of pregnancy recorded for any female subject or for a female partner of a male subject should be reported to the CRO/Vifor Pharma within the same timelines as a SAE, i.e., immediately (within 24 hours of awareness). The Investigator should complete a Vifor Pharma Report on Exposure to Medicines During Pregnancy form and forward to the CRO/Vifor Pharma. Complications of pregnancy such as abortion (spontaneous or induced), premature birth or congenital abnormality are considered SAEs and should be reported using the Vifor Pharma SAE form.

All pregnancies occurring in a female subject or the female partner of a male subject within 90 days after discontinuation of investigational product should be reported as though they were an SAE to the CRO/Vifor Pharma.

11. STATISTICAL ANALYSIS

11.1 Statistical Methods

All statistical analyses will be performed using SAS Version 9.0 or later (SAS Institute Inc. SAS/STAT, Cary, NC). Detailed methodology for summary and statistical analyses of the data collected in this trial will be documented in a statistical analysis plan (SAP), which will be finalised prior to database lock. Any deviation from the SAP will be noted and explained in the final study report. All individual data will be listed as measured.

11.2 Sample Size and Power Calculations

To assess the non-inferiority of FCM compared to IS in the proportion of subjects who will have an increase from baseline in Hb of $\geq 2\text{g/dL}$ at any time up to Week 8 (responders), the following assumptions have been made:

- Subjects that will be included in the study will be mainly subjects with GI disorders and women with HUB. The responder rate after IS treatment is expected to be 70%. This is based on the mean of the proportion of responders in the 2 studies described below in IDA subjects with IBD and IDA subjects with HUB respectively.

In study FER-IBD-07-COR, which compared FCM to IS in IDA subjects with IBD, the proportion of subjects who had an increase from baseline in Hb $\geq 2\text{g/dL}$ at Week 8 was 72% in FCM group and 55% in IS group (Per Protocol Set (PPS)). Seventy three percent in the FCM group and 58% in the IS group had an increase of at least $\geq 2\text{g/dL}$ at any time up to Week 8.

In study 1VIT04002/1VIT04003, which compared FCM to oral iron in IDA subjects with HUB, 82% of subjects in the FCM group had an increase from baseline in Hb $\geq 2\text{g/dL}$ at any time up to Week 6. Although no subjects in this study were treated with Venofer, and no other data are available from studies in which HUB patients are treated with Venofer, it has been assumed that Venofer would have the same response rate as FCM in this patient population.

- The non-inferiority margin for the difference in the proportion of responders between FCM and IS was set to -15%. This margin will ensure a treatment effect for FCM ($70 - 15 = 55$) greater than 33%, the upper bound of the 95% confidence interval (CI) of the proportion of responder of an estimated placebo effect, by more than half the effect itself ($33 + 16.5 = 49.5$). The placebo effect was estimated as follows:

In study 1VIT07017 which compared FCM to Standard Medical Care (SMC) in IDA subjects with HUB or post-partum, there were 55 subjects in the SMC group who did not receive any Iron treatment. Of these, 50 had a Hb assessment at Day

30. At Day 30 the proportion of non-treated subjects with an Hb increase ≥ 2 g/dL was 22% (11/50) with a 95% CI from 11% to 33%.

The sample size is based on showing non-inferiority in the difference in the proportion of subjects achieving an increase in Hb of ≥ 2 g/dL at any time up to Week 8 between FCM and IS. Applying a test at a one-sided alpha level of 2.5%, and a -15% non-inferiority margin, 147 subjects per group will have 80% power to detect that FCM is non-inferior to IS with an expected IS responder proportion of 70%. The total sample size is 368 (184 per treatment group), taking into account an estimated drop-out rate of 20% of the randomised subjects.

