2.4 Sample Size Determination

To assess the non-inferiority of FCM compared to IS in the proportion of subjects who will have an increase from baseline in Hb of $\geq 2\text{g/dL}$ at any time up to Week 8 (responders), the following assumptions have been made:

- Subjects that will be included in the study will be mainly subjects with Gastro Intestinal (GI) disorders and women with heavy uterine bleeding (HUB). The responder rate after IS treatment is expected to be 70%. This is based on the mean of the proportion of responders in the 2 studies described below in IDA subjects with inflammatory bowel disease (IBD) and IDA subjects with HUB respectively.

In study FER-IBD-07-COR, which compared FCM to IS in IDA subjects with IBD, the proportion of subjects who had an increase from baseline in Hb $\geq 2\text{g/dL}$ at Week 8 was 72% in FCM group and 55% in IS group (Per Protocol Set (PPS)). Seventy three percent in the FCM group and 58% in the IS group had an increase of at least $\geq 2\text{g/dL}$ at any time up to Week 8.

In study 1VIT04002/1VIT04003, which compared FCM to oral iron in IDA subjects with HUB, 82% of subjects in the FCM group had an increase from baseline in Hb $\geq 2\text{g/dL}$ at any time up to Week 6. Although no subjects in this study were treated with Venofer, and no other data are available from studies in which HUB subjects are treated with Venofer, it has been assumed that Venofer would have the same response rate as FCM in this subject population.

- The non-inferiority margin for the difference in the proportion of responders between FCM and IS was set to -15%. This margin will ensure a treatment effect for FCM ($70 - 15 = 55$) greater than 33%, the upper bound of the 95% confidence interval (CI) of the proportion of responder of an estimated placebo effect, by more than half the effect itself ($33 + 16.5 = 49.5$). The placebo effect was estimated as follows:

In study 1VIT07017 which compared FCM to Standard Medical Care (SMC) in IDA subjects with HUB or post-partum, there were 55 subjects in the SMC group who did not receive any Iron treatment. Of these, 50 had an Hb assessment at Day 30. At Day 30 the proportion of non-treated subjects with an Hb increase ≥ 2 g/dL was 22% (11/50) with a 95% CI from 11% to 33%.

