4.6 Efficacy Analysis

4.6.1 Primary Efficacy Analysis

The primary endpoint is the percentage of subjects achieving an increase in Hb of $\geq 2\text{g/dL}$ (responders) from baseline at any time up to Week 8. The non-inferiority test will be applied to the difference (FCM - IS) between the proportions of subjects meeting the primary endpoint using the PPS and FAS. Non-inferiority will be determined if the lower bound of the 95% CI of this difference is above the non-inferiority margin as defined -15%. The difference in proportions between the FCM and Venofer groups from baseline at any time up to Week 8 and its one-sided 97.5% confidence intervals (CIs) will be computed using the Wilson score method with continuity correction described by Newcombe (1998).

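### The plan says its -15 point margin ensures an FCM response above 49.5%, but that holds only if the true iron sucrose rate is at least 64.5%, and the 70% used for it is half built from FCM's own response

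*Protocol*

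**What the plan says.** Protocol 11.2, repeated in SAP 2.4, expects an IS responder rate of 70%, the mean of two studies.

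- **IBD study, FCM against IS.** On the primary endpoint definition (any time up to Week 8): "Seventy three percent in the FCM group and 58% in the IS group had an increase of at least" 2 g/dL. At Week 8 itself (per-protocol set) the rates were 72% and 55%.
- **Heavy uterine bleeding (HUB) study, FCM against oral iron.** The FCM rate was 82% at any time up to Week 6. There was no IS arm, and the text says no other IS data exist in this population. So "it has been assumed that Venofer would have the same response rate as FCM in this patient population"; SAP 2.4 says the same.

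The 70% is then used twice.

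- **Sample size:** the plan states that "147 subjects per group will have 80% power to detect that FCM is non-inferior to IS"; the test is one-sided at 2.5%, against the 15-point margin.
- **Margin:** "This margin will ensure a treatment effect for FCM" of 70 - 15 = 55. This is compared with 33%, the upper 95% limit for untreated subjects, and with 33 + 16.5 = 49.5%.

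The success rule in SAP 4.6.1, in line with Protocol 11.7.1, concerns the difference alone: "Non-inferiority will be determined if the lower bound of the 95% CI of this difference is above the non-inferiority margin as defined -15" percentage points. Protocol 3.1 makes non-inferiority to IS the sole route to showing FCM efficacy.

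**The concern.** One of the two equally weighted terms in the control rate is the test drug's response, carried over to the comparator. That assumes equality in HUB, in a trial whose question is how far FCM may fall short of IS. It also sits badly with the IBD figures in the same section, where IS was 15 points lower.

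The consequence lies mainly in the margin argument. A margin on a difference fixes no absolute level for FCM; the level moves with the true IS rate. The plan words its conclusion as a guarantee, gives no range for the IS rate, and plans no comparison of FCM's own rate with 49.5%. If IS responds less often than 70%, a non-inferiority result could be read as establishing a level of FCM response that it does not establish.

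**Working it through.** **Inputs.** All are from Protocol 11.2: IS 58% (IBD, any time up to Week 8) and 55% (IBD, Week 8); FCM 73% (IBD) and 82% (HUB); margin 15 points; one-sided alpha 2.5%; 147 evaluable per arm; drop-out 20%; untreated upper limit 33%; benchmark 49.5%. The interval method is from SAP 4.6.1 (Newcombe score interval with continuity correction).

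**1. The plan's own figures.**
- Control rate: (58 + 82)/2 = 70.
- Sample size, equal rates, unpooled variance: n = (1.96 + 0.8416)² × 2 × 0.70 × 0.30 / 0.15² = 146.5, so 147 per arm.
- Drop-out: 147/0.8 = 183.75, so 184 per arm and 368 in total.

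All reproduce. The protocol states no FCM rate for sizing; 147 follows when FCM is also set at 70%.

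**2. When the benchmark is protected.** Success supports FCM > IS - 15. For this to secure 49.5%, IS must be at least 49.5 + 15 = 64.5%. With IBD at 58% and equal weights, IS in HUB must be at least 2 × 64.5 - 58 = 71%, that is, no more than 82 - 71 = 11 points below FCM's rate there.

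**3. Lowest FCM rate the margin admits.**

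| True IS rate | Basis | IS - 15 | Above 49.5%? | Above 33%? |
|---|---|---|---|---|
| 70% | plan | 55% | yes | yes |
| 64.5% | break-even | 49.5% | at the limit | yes |
| 62.5% | illustration: 15-point gap also in HUB, (58 + 67)/2 | 47.5% | no | yes |
| 58% | IBD, primary endpoint definition | 43% | no | yes |
| 55% | IBD, Week 8 only | 40% | no | yes |

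**4. Power at 147 per arm.** Power = Φ[(0.15 - (IS - FCM))/SE - 1.96], with SE = √{[IS(1 - IS) + FCM(1 - FCM)]/147}. The last column is exact binomial enumeration of the SAP interval.

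| IS | FCM | SE | Normal formula | SAP interval |
|---|---|---|---|---|
| 70% | 70% | 0.0535 | 80.1% | 78.7% |
| 62.5% | 62.5% | 0.0565 | 75.7% | 74.6% |
| 58% | 58% | 0.0576 | 74.1% | 73.1% |
| 58% | 73% | 0.0548 | >99.9% | >99.9% |

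**5. Would an absolute criterion on FCM be free?** Suppose FCM's Wilson lower bound also had to exceed 49.5%. By enumeration, the chance of meeting both conditions is 78.7% at 70/70 (no loss), but 50.9% at 58/58, against 73.1% for non-inferiority alone.

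**The case against.** Several points on the other side stand.

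- **The assumption is disclosed.** The plan says openly that no HUB subject received IS and that equality was assumed. But disclosure does not make the margin statement unconditional.
- **58% is a low scenario, not a replacement estimate.** It comes from IBD alone, while the plan expects mainly GI disorders and HUB. The documents give no arm size or interval for it, so one cannot say whether 64.5% is compatible with it. The HUB figure stops at Week 6 and this trial counts to Week 8, so 82% may be low for that group. An IS rate of 64.5% or more is therefore possible; it is not shown.
- **58% is not the only IS rate cited.** 55% at Week 8 is also given. 58% is the only one on the primary endpoint definition.

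A reader might also draw stronger conclusions that the documents do not support.

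- **That the trial is underpowered.** The loss of about 6 points needs FCM to be 58% as well. The study that supplies IS 58% reports FCM 73%, and with that pair power is above 99.9%. Sizing at equal rates ignores that advantage and is conservative in that respect.
- **That the false-positive rate is inflated.** With FCM at 49.5% and IS at 58%, the SAP rule declares non-inferiority in 18.0% of trials. This is not a type I error: the true difference is -8.5 points, inside the margin, and the plan sets its 2.5% on the difference only.
- **That the margin admits a drug no better than no treatment.** Even at IS 58% the admitted level, 43%, is 10 points above the 33% untreated bound. What fails is the plan's stricter benchmark.
- **That FCM should have to pass 49.5% as a second success criterion.** This would change the primary objective and penalise a drug equal to its comparator in a low-responding population, as the 50.9% in the working shows.

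**Conclusion.** The concern holds for the margin statement. The claim that the margin ensures FCM above 49.5% is conditional on a true IS rate of at least 64.5%, and both IS rates in the documents are lower (58% and 55%). At 58% the admitted FCM level falls 6.5 points short of the benchmark (49.5 - 43). This takes the plan's 33% and 49.5% as written and needs no assumption about the true FCM rate. The 62.5% case does need one: that the IBD gap carries over to HUB.

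Power is a secondary matter of reporting, about 74% to 80% over IS rates of 58% to 70% if the arms are equal. The sample size of 147, 184 and 368 contains no error, and the non-inferiority test itself is unaffected. The change should be made because efficacy is to be claimed through non-inferiority alone, and the present wording overstates what that result would show.

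**What to change.** **Protocol 11.2 and SAP 2.4.**
- Replace the guarantee with a statement that the 49.5% benchmark is met only if the true IS rate is at least 64.5%.
- State that 58% (IBD) is the only available IS rate on the primary endpoint definition, and that 70% depends on taking IS as equal to FCM in HUB.
- Give power at 147 per arm and equal rates as about 74% (IS 58%), 76% (62.5%) and 80% (70%).

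**SAP 4.6.1 and Table 14.2.1.1.** As a supportive analysis, and not a second success criterion, report each arm's responder rate with its 95% Wilson interval, and set FCM's lower bound against 49.5%. Pre-specify that, if the observed IS rate is below 64.5%, the report will say that non-inferiority alone does not establish the plan's benchmark.

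**Cost.** Wording in two documents and a small addition to one table; no more subjects and no new data. The stated power looks slightly less favourable, and the efficacy conclusion may carry a caveat if IS responds below 64.5%.

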11.3 Analysis Set

11.3.1 Full Analysis Set

The full analysis set (FAS) consists of all subjects who satisfy the following criteria:

- Randomised to treatment
- Received at least 1 dose of study treatment
- Had at least 1 baseline and post-baseline Hb value.

Subjects will be analysed in the treatment group they were randomised to.

11.3.2 Per-Protocol Set

The PPS consists of all subjects who, in addition to the FAS criteria, had no major protocol violations (as defined in the SAP).

11.3.3 Safety Set

The safety set consists of all randomised subjects who have received at least 1 dose of study medication. The subjects in this group will be analysed based on the treatment they received.

11.4 Background and Demographic Characteristics

All background and demographic data will be described by mean tables (continuous variables) or frequency tables (categorical variables). Medical history will be coded according to a standard dictionary (Medical Dictionary for Regulatory Activities (MedDRA)) and tabulated according to system organ class and preferred term. The MedDRA version to be used will be the latest version available at the time of study initiation.

11.5 Study Medication

Doses of study drug are defined in Table 2 Iron dosing Schedule for FCM subjects and by the Ganzoni formula for IS subjects. If an incomplete dose of study drug was given to the subject for any reason (e.g.: due to leakage or AE) or a different dose

from the planned dose was administered, this should be recorded in the CRF together with the reason. The dose of study drug received and the number of injections/infusions received will be tabulated for each subject and summarised by treatment group, by visit and overall. Treatment compliance will be calculated for each subject by the percentage of study drug received compared to the planned dose and summarised by treatment group by visit and overall.

11.6 Concomitant Therapy

At each visit, the Investigator will obtain and record any information about concomitant illnesses and any therapeutic interventions (e.g., drug therapy, surgery, etc.) Concomitant medications will be coded using the World Health Organization Anatomical Therapeutic Chemical Drug Reference List classifications (ATC). Counts and percentages of subject use for each medication by ATC Level 2 and 4 and preferred term will be computed and summarised by treatment group.

11.7 Efficacy Evaluations

11.7.1 Primary

The primary endpoint is the percentage of subjects achieving an increase in Hb of ≥ 2 g/dL (responders) from baseline at any time up to Week 8. The non-inferiority test will be applied to the difference between the proportions of subjects meeting the primary endpoint using the PPS. Non-inferiority will be determined if the lower bound of the 95% CI of this difference is above the non-inferiority margin as defined in Section 11.2. Further details will be specified in the SAP.

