9.2.4 Unscheduled Visits

Subjects may be seen at the out-patient clinic for a medical reason related to the VIT-IRON-2011-004 study outside the scheduled visits defined by the protocol. Data collected during such visits must be recorded on the Unscheduled Visit eCRFs designed for this purpose. If the reason for performing an extra visit constitutes a (serious) AE, this information must be documented on the AE pages of the CRF (see Section 10).

10. EVALUATION, RECORDING AND REPORTING OF AEs AND SAEs

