10.2.6 Clinical Laboratory Evaluations

A change in the value of a safety laboratory investigation can represent an AE if the change is clinically significant and clinically relevant or if, during treatment with the

investigational product, a shift of a parameter is observed from a normal value to a pathological value, or a further worsening of an already pathological value. When evaluating such changes, the extent of deviation from the reference range, the duration until return to the reference range, either while continuing treatment or after the end of treatment with the investigational product, and the range of variation of the respective parameter within its reference range, must be taken into consideration.

If, at the end of the treatment phase, there are pathological laboratory values which were not present at baseline, further clinical or laboratory investigations should be performed until the values return to within reference range or until a plausible explanation (e.g., concomitant disease) is found for the pathological laboratory values.

The Investigator should decide, based on the above criteria and the clinical condition of a subject, whether a change in a laboratory parameter is clinically significant and clinically relevant and therefore represents an AE. If the Investigator considers such an AE as serious (e.g., medically significant event fulfilling criteria as per Section 10.1.5, Serious Adverse Event) it must be reported as an SAE.

Iron parameters such as serum iron, TSAT, UIBC, serum ferritin, serum transferrin, Hb, and reticulocytes are expected to be out of range after administration of IV iron products, and will therefore not be considered as AEs. They can be classed as clinically significant but are usually not clinically relevant and therefore are not reported as AEs.

If a laboratory abnormality meeting the above criteria is a sign of a disease or syndrome only the diagnosis should be recorded in the CRF.

If a laboratory abnormality meeting the above criteria is not a sign of a disease or syndrome, the abnormality itself should be recorded in the CRF, along with a descriptor indicating if the test result is above or below the normal range (e.g., “elevated potassium,” as opposed to “abnormal potassium”).

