4.1.3 Planned Assessment Windows

Table 3 describes the Planned Assessment Windows that will be used in all analyses.

Table 3: Planned Assessment Windows

Visit Label	Planned Visits (Protocol Specified)	Analysis Assessment Window	Target Day
Baseline (Day 1)	--	<=1 Day	1
Week 2	± 3 days	from Day 2 to Day 21	14
Week 4	± 3 days	from Day 22 to Day 35	28
Week 6	± 3 days	from Day 36 to day 49	42
Week 8	± 4 days	>= Day 50	56

All assessments will be re-mapped into the analysis windows. For a parameter, if several assessments fall into the same analysis window, the closest to the target day will be considered for the analysis. When there are 2 assessments closest to the target day, the latest one will be considered for the analysis.

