STUDY DRUG DEVIATION	STUDY DRUG DEVIATION # 1	Incorrect IMPs storage condition (FCM store > 30°C or freeze / IS store < 4°C or > 25°C or freeze)	TBD*
	STUDY DRUG DEVIATION # 2	Incorrect treatment administration vs randomization	Major
	STUDY DRUG DEVIATION # 3	Study drug not stopped when subject experienced any kind of hypersensitivity reaction related to the study drug during administration	Major

Vifor DVSCAT (Categories of PDs)	Vifor DVDECOD (Sub-Categories of PDs)	Details	Major or Minor
PROHIBITED MEDICATION	PROHIBITED MEDICATION	Prohibited Therapy and Concomitant Treatment (Oral or other IV iron therapy (other than the study medication), multivitamins or nutritional supplements containing iron > 75 mg per day, ESAs, Blood transfusions)	Major
PROCEDURE/TEST NOT DONE	PROCEDURE/TEST NOT DONE # 1	Vital Signs missing	Major
	PROCEDURE/TEST NOT DONE # 2	Physical Examination missing (Fully missing is Major at Screening/Fully missing is Minor at EOS/Partially missing is Minor at Screening and EOS)	Major/Minor
	PROCEDURE/TEST NOT DONE # 3	Laboratory tests: Haematology & Iron status missing from Visit 2 to Visit 6(Missing assessment is major/Missing parameter is minor)	Major/Minor
	PROCEDURE/TEST NOT DONE # 4	Laboratory tests: Haematology & Iron status missing at Visit 1(Missing assessment is major/Parameters Hb, MCH, MCV, MCHC, Serum Ferritin, TSAT missing is major/Other parameters missing is minor)	Major/Minor
	PROCEDURE/TEST NOT DONE # 5	Laboratory tests : Chemistry missing from Visit 2 to Visit 6 (Missing assessment is major/Missing parameter is minor)	Major/Minor
	PROCEDURE/TEST NOT DONE # 6	Laboratory tests: Chemistry missing at Visit 1(Missing assessment is major/Parameters CRP, ALT, AST missing is major /Other parameters missing is minor)	Major/Minor
	PROCEDURE/TEST NOT DONE # 7	Laboratory tests at planned visits: Urinalysis missing (Missing assessment is major/Missing parameter is minor)	Major/Minor
	PROCEDURE/TEST NOT DONE # 8	Laboratory tests: Hepatitis B and C missing at Visit 1 (Any parameters missing is major)	Major
	PROCEDURE/TEST NOT DONE # 9	ECG missing	Minor
	PROCEDURE/TEST NOT DONE # 10	Laboratory tests: Pregnancy Test at Screening missing	Major
	PROCEDURE/TEST NOT DONE # 11	Laboratory tests: Pregnancy Test at Visit 6 missing	Major
PROCEDURE OUTSIDE WINDOW	PROCEDURE OUTSIDE WINDOW # 1	Laboratory tests Out Of planned Window	Minor
	PROCEDURE OUTSIDE WINDOW # 2	Vital Signs out of planned window	Minor

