	PROCEDURE OUTSIDE WINDOW # 3	ECG Out Of planned Window (Not done at Screening & Week 4 & EOS)	Minor
NON- COMPLIANCE WITH PROCEDURE	NON-COMPLIANCE WITH PROCEDURE #1	Dosing NOT performed after all study assessments for the visit(Out of chronological order is minor)	Minor
	NON-COMPLIANCE WITH PROCEDURE #2	Missing reporting of SAEs to sponsor within the agreed timeframe "within 24 hours of awareness"	Major
VISIT OUTSIDE WINDOW	VISIT OUTSIDE WINDOW # 1	Screening duration > 7 days	Minor
	VISIT OUTSIDE WINDOW # 2	visits out of window (Planned chronological visits schedule not respected is major)	Major
VIST NOT DONE	VISIT NOT DONE	Visits NOT done	Major

Vifor DVSCAT (Categories of PDs)	Vifor DVDECOD (Sub-Categories of PDs)	Details	Major or Minor
SUBJECT NOT WITHDRAWN AS PER PROTOCOL	SUBJECT NOT WITHDRAWN AS PER PROTOCOL	Site staff failed to take the appropriate action in response to protocol-specific discontinuation/withdraw criteria such as: severe anaemia (Hb <6 g/dL) and the subject continued the study	Major
OTHER	NON-COMPLIANCE WITH PROCEDURE # 1	Rescreening within 4 weeks of original screening visit(minor)	Minor
	NON-COMPLIANCE WITH PROCEDURE # 2	Race is not Chinese and subject randomized (minor)	Minor
	OTHER	Any other protocol deviation (e.g., as outlined in the monitoring plan):	TBD*
NOTE		*TBD (to be discussed): PDs will be determined of major or minor by TMM and consult with Sponsor if necessary CRA will submit the signed and dated major protocol deviation to local EC within 15 working days.	

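### The SAP's Week 8 window has no last day, so an Hb taken after the endpoint period can make a responder: clearly in the FAS, and in the primary PPS only if a late visit counts as a minor deviation

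*Protocol*

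**What the plan says.** **Endpoint.** Protocol Section 11.7.1 and SAP Section 4.6.1 count a rise in Hb of at least 2 g/dL at any point up to Week 8: "responders) from baseline at any time up to Week 8. The non-inferiority test will be applied to the difference between the proportions of subjects" who meet it. Protocol Table 1 and Section 9.2.3 place the last visit at Week 8 ±4 days.

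**Analysis windows.** SAP Section 4.1.3 gives its windows general scope: "Table 3 describes the Planned Assessment Windows that will be used in all analyses". It then says "All assessments will be re-mapped into the analysis windows". The Week 8 row starts at Day 50 and has no end; its target is Day 56. If a window holds more than one value, "if several assessments fall into the same analysis window, the closest to the target day will be considered for the analysis". SAP Section 4.6.1 adds no cut-off day for the responder definition.

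**Analysis sets.** The primary test is on the PPS, with the FAS as sensitivity analysis (SAP Section 4.1.6). SAP Section 4.6.1 applies the same non-inferiority test to both. The PPS drops subjects with major violations.

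**Deviation classes.** SAP Appendix 1 rates "Laboratory tests Out Of planned Window" as Minor. It rates "visits out of window (Planned chronological visits schedule not respected is major") as Major. It rates a visit not done as Major, and likewise a missing haematology assessment from Visit 2 to Visit 6.

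**Off-schedule values.** Protocol Section 9.2.4 allows visits for a medical reason "outside the scheduled visits defined by the protocol" and has their data recorded.

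**The concern.** The endpoint has an end and the window that supplies its last value does not. If a subject's end-of-study visit slips by two or three weeks, or the only sample after Day 49 comes from a later unscheduled visit, the SAP treats that Hb as a Week 8 value. It then feeds the any-time responder definition, the Week 8 responder rate and the Week 8 contrast in the repeated-measures models.

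Follow-up length matters here. Protocol Section 2.3.1 chose eight weeks because iron sucrose takes longer to deliver and control subjects need time to respond. Extra time for some subjects is extra opportunity to reach 2 g/dL. The trial is open-label: Hb is an objective measurement, but the date of the last visit is not protected from knowledge of the arm.

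**Working it through.** **1. Window limits (SAP Table 3, days from target)**

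| Visit | Window | Target | Before | After |
|---|---|---|---|---|
| Week 4 | 22–35 | 28 | −6 | +7 |
| Week 6 | 36–49 | 42 | −6 | +7 |
| Week 8 | 50 onwards | 56 | −6 | none |

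The same +7 days at Week 8 would end the window on Day 56 + 7 = 63. The protocol's ±4 days around Day 56 gives Days 52–60.

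**2. Which subjects are exposed**

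| Situation | FAS | PPS |
|---|---|---|
| On-time Week 8 Hb, plus a later value | Protected if only window-selected values count | Same |
| Week 8 visit late, no other Hb after Day 49 | Late value counts | Counts only if the late visit is Minor |
| Week 8 visit missed, later unscheduled Hb | Late value counts | Subject excluded (Major) |

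The first row is conditional because the SAP does not say whether the any-time definition uses one selected value per window or every Hb. If it uses every Hb, the closest-to-target rule gives no protection.

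**3. The plan's own sample size**

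Inputs from Protocol Section 11.2: 70% response in IS, margin 15 points, one-sided 2.5%, 80% power. Equal true rates are taken.

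n = (1.960 + 0.842)² × 2 × 0.7 × 0.3 / 0.15² = 146.5, so 147 per group. With 20% drop-out, 147 / 0.8 = 183.75, so 184 per group and 368 in total. The stated figures reproduce, and closing the window does not change them.

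**4. Possible size (assumed rates)**

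The documents give no number of late Week 8 samples. Assume 30% non-responders, that is 0.30 × 147 ≈ 44 per arm. Let L be the share of these whose only value in the window is late, and C the share of those who then cross 2 g/dL. The points added to an arm are 30 × L × C.

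| L | C = 25% | C = 50% | C = 100% |
|---|---|---|---|
| 2% | 0.15 | 0.30 | 0.60 |
| 5% | 0.38 | 0.75 | 1.5 |
| 10% | 0.75 | 1.5 | 3.0 |

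In subjects this is about 0.2 to 4.4 per arm. One subject is 1/147 = 0.68 points; in a FAS of at most 184 per arm it is at least 1/184 = 0.54 points.

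**5. Effect on the decision**

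The SAP interval is Newcombe's, with continuity correction. Its lower limit is d − √[(p₁ − l₁)² + (u₂ − p₂)²], where 1 is FCM, 2 is IS, and l and u are the single-arm Wilson limits. A deliberately borderline case is FCM 97/147 and IS 103/147:

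p₁ = 0.6599, l₁ = 0.5766, p₂ = 0.7007, u₂ = 0.7719, d = −0.0408.
Lower limit = −0.0408 − √(0.0833² + 0.0712²) = −0.1504.

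| Extra responders (FCM, IS) | Lower limit | Non-inferior? |
|---|---|---|
| 0, 0 | −15.04% | No |
| 1, 1 | −14.98% | Yes |
| 3, 3 | −14.86% | Yes |
| 3, 0 | −12.95% | Yes |
| 0, 3 | −16.95% | No |

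Equal late conversion leaves the difference unchanged and narrows the interval slightly. Unequal conversion moves the limit either way.

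**The case against.** The strongest reply is that the primary analysis is largely shielded. A subject who misses Week 8 leaves the PPS. If every out-of-window visit is Major, a subject with a late one leaves too, and a site that delayed a visit would only remove its own subject from the primary set. This stands for missed visits. For late visits it depends on an unclear line: the parenthesis can be read as limiting Major to visits out of order, and a late laboratory test by itself is Minor. It does not help the FAS.

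Two further limits stand in part. The closest-to-Day-56 rule protects subjects with an on-time sample wherever window-selected values are used. SAP Section 3.3 also disregards efficacy values after prohibited medication starts, in both sets. That works for recorded use; concomitant medication is defined only to the end of the study, so the gap is confined to samples after the end-of-study visit.

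A reader might infer more than the documents support:

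- **That late Hb values will be routine.** Protocol Section 10.2.6 says "further clinical or laboratory investigations should be performed until the values return to within reference range", but this concerns pathological values absent at baseline. Low Hb was present in every eligible subject. No Hb is scheduled after Week 8, and Protocol Section 4.2 puts participation at 10 weeks at most.
- **That the open window favours FCM.** If iron sucrose is the slower arm, late values could raise the control rate and make non-inferiority harder to show.
- **That every late conversion is spurious.** Some of these subjects will already have crossed 2 g/dL by Day 60.

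**Conclusion.** The defect is real but limited. SAP Table 3 contradicts the endpoint period, and nothing in SAP Section 4.6.1 corrects it. The FAS non-inferiority analysis and the FAS Week 8 secondary endpoints are clearly exposed. The primary PPS is exposed only for late, not missed, Week 8 visits, and only if these are handled as minor deviations.

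The size is unknown and probably small. The range of 0.15 to 3.0 points per arm rests wholly on assumed rates of lateness and late conversion, and the borderline example was chosen to show sensitivity, not as a forecast. The direction is not fixed. The documents do not support the stronger conclusion that the primary result is unreliable or tilted towards FCM. The change is still worth making, because a few late values could decide a close result and the rule is easy to settle before database lock.

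**What to change.** 1. **SAP Table 3:** give the Week 8 window a last day. Day 63 matches the Week 4 and Week 6 windows but still admits Days 61–63; Day 60 is the protocol's own limit. Either resolves the point if stated in advance.
2. **SAP Section 4.6.1:** state that Hb values after that day are listed only and do not count for the primary responder definition or the Week 8 endpoints. State whether the any-time definition uses window-selected values or every eligible Hb.
3. **SAP Appendix 1:** reconcile the entries for late laboratory tests and late visits, so that PPS membership after a late Week 8 visit is unambiguous.
4. **Sensitivity analysis:** repeat the responder analysis with the late values included.

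The cost is one table cell, a few sentences and one extra table. A few late values move to listings. A subject with only a late value is classified from earlier visits, which may miss a response between the last earlier sample and the cut-off; item 4 shows how much that matters. Sample size and alpha are unchanged.
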